## Identifying Participants

**Overview of initial screening procedures.** It is possible that all participants will be patients at the Comprehensive Care Practice (CCP). CCP is located in the Mason F. Lord Building at the Johns Hopkins Bayview Medical Center in Baltimore, MD. CCP provides primary medical care to ~450 HIV+ adults and will serve as the primary recruitment site. However, over the course of this research we will attempt to identify possible recruitment sites within the State of Michigan. If we identify sites within Michigan, we will seek WMU IRB approval for those sites prior to initiating recruitment from those sites. Recruitment procedures across the sites will be as similar as possible given local resource constraints. Any differences will be specified concurrently with seeking approval for the new site(s).

Participants will be recruited from their regularly scheduled HIV care appointments at which current viral load and CD4 counts are evaluated. Anyone who is HIV positive who meets the criteria for substance use disorder will be told by their doctor about our research study and given a recruitment flyer that explains the nature of participation.

**Script for physician:** *I am conducting a research study with my colleagues that may be of interest to you. The research study is testing a way to help people living with HIV take their antiretroviral medicines according to their prescriptions. The study provides \$50 per month for participating in an interview and showing the interviewer your pill bottle. Some people in the study will also get money for taking their medication. Here is a flyer about the research study. If it seems like something that might interest you, then you can talk to the outreach coordinator today. She can tell you more about the study and will ask you a few questions to determine if the study is right for you. I want to stress that participating in this*

*research is optional, and that your care at Johns Hopkins will not be affected in any way by your decision to participate or not participate. Would you like to talk to the outreach coordinator to learn more about it?*

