**Transportation to the Intake Appointment.** Should the participant be unable to immediately attend the intake appointment following the initial screening, the participant should be assisted in developing a plan to attend the appointment. We cannot provide financial assistance to make this happen, but we do provide a reloadable gift card with an initial value of \$50 to everyone who completes their intake interview, independent of whether they qualify or choose to continue and be randomly assigned to one of the study groups. If a participant is unable to complete the intake assessment through no fault of their own (e.g., technical malfunction) and must return, they will be compensated \$20 for the return trip.

**Procedures for Initiating the Intake Assessment.** Once the participant has arrived for the intake assessment, the outreach coordinator will obtain the CD4/RNA counts, substance abuse history, and depression diagnosis from the participant's primary physician. The outreach coordinator will print out the following materials:

1) [Inclusion/Exclusion Checklist](#); 2) [Smartphone Assessment](#); 3) [Study Consent Form](#); 4) [HIPAA form](#); and 5) [Material Acknowledgement Form](#). The outreach coordinator will contact the WMU staff to inform them that the participant has arrived and give them the CD4/RNA counts, the substance abuse history, and depression diagnosis of the participant. The outreach coordinator will then

initiate the Smartphone Assessment. If the participant meets inclusion criteria, the outreach coordinator will escort him/her to the assessment station on the second floor of CLH. If the participant is excluded, the outreach coordinator should ask if the participant needs bus tokens and dismiss them. The outreach coordinator will set the participant up at the assessment computer to begin the informed consent process. The assessment computer is under the control of the WMU staff using [TeamViewer](#) remote control software.

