### **Analytic plan for SteadyRx study**

Descriptive statistics (means and standard deviations or proportions) will be calculated for demographics, baseline participant factors (e.g., quality of life, substance use), treatment history, health literacy, and application ratings and engagement. All analyses will be intent to treat; all participants who are randomized will be included. All analyses will be adjusted for the pre-specified covariates used for stratification. All hypothesis tests will be two-sided,  $\alpha$  will be set at 0.05, and p-values for secondary analyses will be corrected to maintain  $\alpha=0.05$ . Based on our past research and the automated collection of our primary outcome measure, we expect relatively little missing data and little difference in the rates of missing data across groups. We plan to conduct analyses in which missing samples are assumed to represent the adverse outcome (e.g., missing = drug positive) and in which missing data will be ignored (missing = missing). The “missing positive” method is more conservative and will be considered the primary method.

Primary Outcomes. The effects of the intervention relative to the control group on the dichotomous monthly adherence measure will be analyzed with a longitudinal logistic regression model with treatment group and time as covariates. The group term, representing the between-group difference averaged over time, will be the primary coefficient of interest. Correlation among outcomes over time within individuals will be handled using the method of Generalized Estimating Equations (GEE). The dichotomous viral load variable (<400 HIV-RNA/mL, y/n) will be modeled with an analogous model but with only two follow-up measures.

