Secondary and Exploratory Analyses. Continuous measures assessed repeatedly over time (bottle openings, CD4, HIV-1 RNA, and MOS-HIV) will be analyzed using a longitudinal linear regression model, analogous to that used for the primary outcomes. We will control for baseline values in the CD4, viral load, and MOS-HIV models. Measures assessed only at intake will be analyzed via linear or logistic regression as appropriate. Baseline predictors of response to treatment, including positive urine screen for cocaine or opioids, health literacy (TOFHLA), depression (BDI), psychological factors (SCL-90), job and educational history (VEA), and executive function (Wisconsin Card Sorting) will be assessed by fitting regression models with interactions between treatment assignment and each predictor variable, to determine if the effect of treatment on outcome varies as a function of each of these predictors. Similar models, with an interaction between treatment group and drug use, adherence to buprenorphine/methadone, and attendance to primary care, respectively, (as time-varying covariates) will allow us to determine whether these variables affects response to treatment.

Usage, Acceptability, and Cost. Acceptability and SUMI global scale scores, app uses per day, daily duration of use, and cost of the app and incentives and ICER will be summarized via descriptive statistics (mean, SD, medians, histograms).

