### **Data Analysis to be reported in future publication**

Groups were compared on intake variables using Fisher’s exact tests for dichotomous variables, chi-square tests for categorical variables with more than two categories, and t-tests for continuous variables. Outcome measures were analyzed using generalized estimating equations (GEE) (Zeger, Liang, & Albert, 1988), including and excluding the stratification variables as covariates. GEE results presented use the covariate model unless otherwise specified. Planned comparison t-tests were used to compare between and within groups on outcome measures at time points 1 and 6. Analyses were intent-to-treat and conducted using SAS version 9.3. Missing data were treated as missing-missing. Analyses were two-tailed with statistical significance set at alpha of .05. Due to the error in the collection of biometric data, analyses for these variables are not included.

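### The primary model for viral load <400 names no baseline viral load, although it is obtained before randomization, and the sentence that might supply it is ambiguous

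*Combined protocol and SAP*

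**What the plan says.** Under Primary Outcomes, the Analytic plan for SteadyRx study gives the monthly adherence analysis as a "longitudinal logistic regression model with treatment group and time as covariates", fitted by GEE. The dichotomous viral-load variable is "modeled with an analogous model but with only two follow-up measures". The general paragraph adds that "All analyses will be adjusted for the pre-specified covariates used for stratification". Under Random Assignment to Study Conditions, those covariates are current depression, recent cocaine or opiate use, and TOFHLA score relative to the rolling median. None of them is a baseline outcome value.

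Under Secondary and Exploratory Analyses, just after a list of continuous repeated measures, the plan says: "We will control for baseline values in the CD4, viral load, and MOS-HIV models".

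Baseline HIV-1 RNA is available in time. Participants are recruited from "regularly scheduled HIV care appointments at which current viral load and CD4 counts are evaluated". At intake "the outreach coordinator will obtain the CD4/RNA counts, substance abuse history, and depression diagnosis". The Procedure paragraph of the random-assignment section has the RNA level phoned through before the principal investigator runs the urn. The paragraph on CD4 counts and HIV-1 RNA levels expects one baseline and two study-period measures.

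The closing section, Data Analysis to be reported in future publication, describes GEE "including and excluding the stratification variables as covariates" and names no baseline outcome. It adds: "Due to the error in the collection of biometric data, analyses for these variables are not included".

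**The concern.** Baseline suppression is usually a natural predictor of later suppression, and the trial already plans to hold it. Eligibility requires neither a detectable viral load nor poor adherence, so the sample can mix suppressed and unsuppressed people. The urn does not balance on viral load. With about 25 per arm the groups can start apart by chance, and a model with only group, time and the stratifiers cannot separate that difference from a treatment effect. Power may also be lost. Because the plan can be read either way, the choice of primary model could be made after the data are seen.

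**Working it through.** The documents give no power, event rate or effect size, so there is no stated figure to reproduce. From the documents: N = 50, near-equal allocation, two follow-up viral loads, two-sided alpha 0.05. Everything else below is an assumption.

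**1. Chance imbalance (exact).** Let X₁ and X₀ be independent Binomial(25, p) counts of participants suppressed at baseline. A gap of 20 points is 5 of 25 people, so the quantity is P(|X₁ − X₀| ≥ 5). The SD of the difference in proportions is √(2p(1−p)/25).

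| p | SD of difference | P(gap ≥ 20 points) |
|---|---|---|
| 0.5 | 0.141 | 20.3% |
| 0.6 | 0.139 | 19.3% |
| 0.8 | 0.113 | 11.0% |

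This assumes simple randomization. If the stratifiers predict viral load, urn balancing removes part of the gap, so these are upper-end values.

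**2. Power with and without baseline <400.** Simulated logistic GEE: exchangeable correlation, 25 per arm, two visits, 6,000 trials per cell. The base model has group, linear time and three binary stratifiers. Baseline suppression is 60%. The test uses the Mancl-DeRouen variance with a t reference. Here r is the correlation of the latent baseline with the person's random intercept. It is not the correlation an analyst would see: at intercept SD 2, r = 0.3 / 0.5 / 0.7 gives an observed binary baseline-outcome correlation of about 0.14 / 0.24 / 0.33. Effects are log-odds, and control suppression is about 44% unless stated.

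| Intercept SD, effect | r = 0.3 | r = 0.5 | r = 0.7 |
|---|---|---|---|
| 2, 2.0 | 59.0 → 58.2% | 59.3 → 61.1% | 58.1 → 63.5% |
| 3, 2.2 | 39.9 → 38.9% | 38.3 → 39.8% | 38.9 → 45.2% |
| 1, 1.0 | 35.9 → 34.7% | 35.5 → 35.0% | 36.4 → 37.1% |
| 2, 2.0, control 60% | 52.1 → 50.2% | 51.5 → 52.2% | 52.5 → 55.9% |

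The changes run from −1.9 points (52.1 to 50.2) to +6.3 (38.9 to 45.2). A further run at r = 0.9 gave about +12. With 10% of outcomes missing and set to adverse (the plan's primary rule), and 10% of baselines absent and filled with the pooled mean, the changes at SD 2 are −2.0, 0.0 and +2.7 points.

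A second simulation used a different data-generating model, independence working correlation and no stratifiers in either model, with conditional log-odds ratio 1.5. Control suppression at follow-up was set by baseline status (suppressed / not). The implied correlation is φ = (difference)·√(0.6·0.4 / (m(1−m))), where m is the mean control rate.

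| Follow-up rates | φ | Power, without → with |
|---|---|---|
| 65 / 45% | 0.20 | 67 → 67% |
| 75 / 35% | 0.40 | 56 → 62% |
| 85 / 25% | 0.60 | 38 → 52% |
| 90 / 15% | 0.75 | 22 → 38% |

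In the last row about 6% of fits were unstable and were excluded.

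**3. What an uncorrected gap does.** With no true effect (SD 2), consider trials where SteadyRx starts 20 or more points ahead, about 19.3% / 2 = 9.7% of trials at p = 0.6. The mean estimated log-odds ratio is 0.19 / 0.26 / 0.39 without the covariate at r = 0.3 / 0.5 / 0.7, and 0.03 / −0.01 / −0.01 with it. False wins for SteadyRx (nominal 2.5%) are 3.7 / 3.7 / 6.1% without and 1.5 / 1.5 / 1.7% with, using Mancl-DeRouen and t. Under an uncorrected z test the covariate lowers false wins only to about 4–5%.

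**4. Overall type I error.** With the uncorrected sandwich and z, the viral-load model without the covariate gives 6.1–6.4% (5.4–5.8% in a separate rerun), and 6.6–6.7% with it. The adherence model without it gives 6.4–6.6% (about 7% in the rerun). With Mancl-DeRouen and t, all are about 3%.

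**The case against.** The best counter-argument is that the baseline is already planned. The sentence in the secondary section says viral load, which is the Primary Outcomes paragraph's name for the dichotomous variable, while the continuous measure has just been called HIV-1 RNA. That reading is tenable. A reader might conclude that the plan definitely omits the baseline from this primary model; the documents do not support that. The sentence's position among continuous secondary measures leaves the matter open, and one phrase would settle it.

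A reader might also infer that the adherence model neglects an available baseline. It does not. The MEMS cap is handed over after assignment, so no pre-randomization MEMS value exists, and the intake Visual Analog Scale is completed after the draw. Viral load as a stand-in for on-time bottle openings is an idea from outside the plan, and its worth rests on an assumed association.

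Three further points stand. The protocol argues for few stratification variables at this sample size, and similar caution applies to covariates. The benefit is small or negative over much of the simulated range. The reported biometric collection error may have reached the baseline values; the documents do not say. What survives is the ambiguity, and the lack of protection against a chance gap if the narrower reading is followed.

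**Conclusion.** The concern holds for the viral-load co-primary outcome, as a gap in specification of modest size. As written, the model can be fitted without a baseline that the trial planned to collect before randomization. The imbalance probability is exact under simple binomial sampling. The power change, from about −2 to about +6 points and higher only with a stronger baseline-outcome association, depends wholly on assumed rates, effects and correlations.

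It would be tempting to say that the omission biases the trial or inflates its overall type I error. Neither follows. Randomization protects the unconditional comparison, and the shift appears only after conditioning on an observed imbalance. The type I error somewhat above 5% comes from the uncorrected sandwich variance with 50 participants; it is present without the covariate and slightly larger with it. Nor is a power gain assured.

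**What to change.** If the baseline values are not affected by the collection error:

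- In Primary Outcomes, add pre-randomization viral load <400 (y/n) to the dichotomous viral-load model.
- In Secondary and Exploratory Analyses, state that the baseline sentence covers both the dichotomous and the continuous viral-load models.
- Report the stratifier-only model alongside, name it as the fallback if the fit fails, and say which odds ratio is primary.
- For MEMS adherence, use baseline viral load at most as a sensitivity covariate.

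Whether or not the baseline values are usable, state a small-sample correction for the GEE sandwich variance. Leave the choice to the trial statistician: Mancl-DeRouen with t is conservative (about 3% type I error) and cost over 10 points of viral-load power against the uncorrected test in simulation.

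The closing data-analysis section is in the past tense. If outcomes have already been seen, label the baseline-adjusted model a sensitivity analysis.

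The cost is SAP wording, with no new data and no change to intake. The downsides are one more parameter in a 50-person model, possible sparse cells, a power loss of up to about 2 points if baseline is weakly prognostic, and a conditional odds ratio that differs from the less adjusted one.

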### Design

This randomized controlled pilot study features a parallel group design. Participants (N = 50) will be randomly assigned to one of the two groups: Treatment as usual (TAU) or the SteadyRx-supported antiretroviral adherence group (SteadyRx). We will randomize using urn stratification to promote equal numbers of individuals in each group and balanced distributions within a dichotomized covariate expected to be associated with the outcome. Stratification variables are current depression (Y/N); self-report of problem drug use in the last 30 days (Y/N); and TOFHLA score  $\leq$  the rolling median (Y/N). Study participation will last for six months from the date of randomization.

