## Secondary Outcome Variables

Secondary Measures. (1) Monthly percentage of on-time (i.e., within three hours of the scheduled time set by patient-physician agreement) bottle openings as measured by MEMS and self-report, respectively. Note that this is different from the primary measure which dichotomizes adherence (Y/N) with a 95% threshold. The primary measure is the measure of greatest clinical significance. The secondary measure is more sensitive to changes in behavior; (2) CD4 counts and HIV-1 RNA levels obtained at primary care visits.

Exploratory Measures. (1) MOS-HIV physical health and mental health summary scores (0-100) across the study period; (2) self-reported days of opiate and cocaine use.

Usage, Acceptability, and Cost Measures. Outcomes related to the usage and acceptability of the Smartphone application will include Acceptability Questionnaire total score, SUMI global scale score, average uses per day, and average duration of use per day. Outcomes related to the cost of the intervention will include total cost of the intervention per person, and the incremental cost-effectiveness ratio (ICER). To calculate ICER, we will divide the costs of the intervention by the difference between the two groups in terms of the percent of participants who take 95% of prescribed doses of their antiretroviral medication. The ICER can be interpreted as dollars spent per unit of desired outcomes gained. In addition, a more complete cost/benefit analysis conducted by academic economists will be included in a future large-scale study.

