**Inclusion/Exclusion Criteria:**

Applicants will be eligible to participate in the study if they:

- a) Are 18 to 100 years old
- b) Are HIV positive
- c) Have a primary care physician who is providing their HIV-related care including prescribed ART
- d) Meet criteria for substance use disorder
- e) Speak fluent English
- f) Can operate a smartphone

Applicants will be excluded if they:

- a) Report current suicidal ideation. **Immediately initiate suicide prevention protocol in accordance with CCP policy/practices.**
- b) Report auditory or visual hallucinations. **Immediately alert study doctor if a participant has active hallucinations.**
- c) Are currently participating in any other HIV/AIDS related or medication adherence related research studies.

**Informing Participants of Eligibility/Ineligibility.** The applicants should never be told why they are eligible or ineligible. This policy will prevent the community from learning about the eligibility criteria. This is imperative, since knowledge of the study criteria could result in applicants either falsely self-reporting characteristics in an effort to get admitted to the study. All staff members should be intimately familiar with the policies related to eligibility described in this treatment manual.

**The Intake Interview.** The interview will be conducted by using the [SteadyRx Intake Assessment Checklist – Outreach Coordinator](#) and the [Intake Assessment Checklist – WMU Staff](#). This interview includes the Smartphone Assessment Protocol, the Testing of Functional Health Literacy in Adults (TOFHLA), the Beck Depression Inventory (BDI-II), the Visual Analog Scale for self-reporting ART adherence, the Medical Outcomes Study HIV Health Survey, Addiction Severity Index – Lite (ASI- Lite), and the Patient Reactions Assessment.

The [Smartphone Assessment Protocol](#) assesses whether participants can operate a smartphone.

The [Test of Functional Health Literacy in Adults](#) (TOFHLA) – a standard measure of health literacy which has been shown to predict ART adherence.

The [Visual Analog Scale for self-reporting ART adherence](#) which has been recommended as providing the highest quality self-reports of ART adherence in several recent studies.

The [Medical Outcomes Study HIV Health Survey](#) is a widely used assessment of quality of life for HIV/AIDS patients that assesses perceived physical and mental health.

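### The plan adjusts for intake values in the CD4, viral load and MOS-HIV models but not for intake self-reported adherence, and it adjusts drug-use days only for a yes/no form of recent use

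*Combined protocol and SAP*

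**What the plan says.** All references are to the combined protocol and SAP.

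- *Secondary Outcome Variables* makes the monthly percentage of on-time dosing a secondary outcome, "as measured by MEMS and self-report, respectively". It lists "self-reported days of opiate and cocaine use" as an exploratory outcome.
- *Analytic plan for SteadyRx study* (secondary and exploratory analyses) puts bottle openings, CD4, HIV-1 RNA and MOS-HIV into a longitudinal linear model. It then says: "We will control for baseline values in the CD4, viral load, and MOS-HIV models". Drug-use days are not among the modelled measures. Self-reported adherence is there only if bottle openings is read to include its self-report version.
- The same section adjusts every analysis for the stratification covariates. Under *Random Assignment to Study Conditions* these are current depression, recent cocaine or opiate use (yes/no), and a health literacy score at or below the rolling median.
- The intake interview includes "the Visual Analog Scale for self-reporting ART adherence, the Medical Outcomes Study HIV Health Survey", and also the ASI-Lite. *Elements of the monthly assessments* repeats all three instruments at each of the six monthly visits.
- *Data Analysis to be reported in future publication* describes GEE models with and without the stratification variables. It names no baseline outcome value as a covariate.

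**The concern.** The three adjusted outcomes all have a value from before the intervention. Electronic bottle openings have none, because the cap is first issued at intake, so their absence from the list makes sense. That reason does not cover the VAS, which belongs to the same block of surveys as MOS-HIV: one is adjusted for its intake score and the other is not. For drug use, the yes/no covariate cannot separate a participant with two days of use from one with 28.

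In a trial of this size ("Participants (N = 50) will be randomly assigned to one of the two groups"), intake differences between arms are likely by chance. Without the intake value in the model, about rho times such a difference carries into the estimated group effect, where rho is the correlation of intake with follow-up. The variation between participants that intake would explain stays in the error term.

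**Working it through.** **Inputs from the documents.** N = 50. Near-equal arms are intended ("We will randomize using urn stratification to promote equal numbers of individuals in each group"), so I take 25 per arm. There are six monthly follow-up visits. The documents give no standard deviation, power statement or intake-to-follow-up correlation for these outcomes, so there is no figure of the plan's own to reproduce.

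**Assumptions.** Outcomes are in SD units, the correlation rho is the same between any two visits including intake, and the group effect is averaged over six visits. I show rho = 0.3, 0.5 and 0.6.

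**1. VAS, before any credit for the stratification covariates.**
- Variance of a participant's six-visit mean: V = (1 + 5·rho)/6.
- Share explained by intake: R² = rho²/V.
- Standard error ratio, adjusted to unadjusted: √(1 − R²).
- Equivalent unadjusted sample size: 50/(1 − R²).

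| rho | V | R² | SE ratio | SE reduction | Equivalent N |
|---|---|---|---|---|---|
| 0.3 | 0.417 | 0.216 | 0.885 | 12% | 64 |
| 0.5 | 0.583 | 0.429 | 0.756 | 24% | 88 |
| 0.6 | 0.667 | 0.540 | 0.678 | 32% | 109 |

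These are upper figures. The plan itself says that depression, drug use and low health literacy are associated with adherence, so the stratification covariates already explain some of this variance. A fading correlation also shrinks the gain. If follow-up visits correlate at 0.5 with one another but intake correlates with them at 0.3 on average, R² = 0.09/0.583 = 0.154 and the SE ratio is √0.846 = 0.920, a reduction of 8% instead of 24%.

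**2. Drug-use days, after credit for the yes/no covariate.** A normal variable split at its median keeps 2/π = 64% of the intake information. The further SE ratio is √[(1 − R²)/(1 − 0.637·R²)].

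| rho | Further SE ratio | Further SE reduction |
|---|---|---|
| 0.3 | 0.953 | 5% |
| 0.5 | 0.886 | 11% |
| 0.6 | 0.837 | 16% |

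The real covariate is any recent use, not a median split. With a 90/10 split, 34% of the information is kept and the same formula gives further reductions of 8%, 18% and 25%. Day counts are probably skewed, so all of these are indicative only.

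**3. Chance imbalance.** The intake difference between arms has SD √(2/25) = 0.283. If the variable is not balanced by design, the difference exceeds 0.3 SD in 2·[1 − Φ(0.3/0.283)] = 29% of randomizations. A 0.3 SD intake difference shifts the unadjusted group estimate by rho × 0.3 = 0.09, 0.15 or 0.18 SD. The unadjusted standard error, √(2V/25), is 0.183, 0.216 or 0.231, so the shift is about 0.5, 0.7 or 0.8 of a standard error. For drug use the urn balances the yes/no form, so this example applies mainly to the VAS.

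**The case against.** The strongest case against is that this is a precision preference on one secondary and one exploratory outcome in a pilot, and that the plan is not silent on intake drug use. Both parts stand. A reader might infer from the list of three adjusted models that drug-use days are compared with no intake information at all. The documents do not support that: recent cocaine or opiate use is balanced by the urn and adjusted for in every analysis. A reader might also infer that an intake difference passes in full into the result, or that the unadjusted comparison is biased. Only about rho times the difference carries over, and randomization keeps the estimator unbiased.

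Three practical objections also stand and shape the fix.

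- Adding a covariate is not enough where no model is named, which is the case for drug-use days and arguably for self-reported adherence.
- The intake VAS may not be a true baseline. *Assessments* places intake before randomization, but the randomization procedure has the VAS and MOS-HIV completed after the urn is run, when staff know the group and the participant has not yet been told. The adjustment already planned for MOS-HIV has the same weakness.
- It is inferred, not stated, that the ASI-Lite yields the number of days used, and that the VAS captures the self-reported adherence outcome as defined, with its three-hour window.

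Finally, the section on the future publication is written in the past tense. If results are already known, adding covariates now is a post hoc choice.

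None of this explains why MOS-HIV is adjusted for its intake score and the VAS is not.

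**Conclusion.** The point holds as a minor one, limited to secondary and exploratory outcomes. Self-reported adherence is compared without its intake value; drug-use days are compared with a yes/no form of intake use but not the number of days. The cost is lost precision and uncorrected chance imbalance, not bias.

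The size rests on assumed correlations of 0.3 to 0.6 that are equal across visits. On that basis the standard error for the VAS would fall by at most 12% to 32%, and by less to the extent that the stratification covariates already explain the variance or correlation with intake fades. For drug-use days the further fall is about 5% to 16% under the median-split assumption, and it is the less certain of the two. The case is stronger for the VAS. Nothing here bears on the primary adherence and viral load models.

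**What to change.** 1. In the secondary and exploratory analyses of *Analytic plan for SteadyRx study*, add self-reported adherence (VAS) and self-reported days of opiate and cocaine use to the repeatedly measured outcomes that are modelled.
2. Control for the intake value of each as a continuous covariate, alongside group, time and the stratification covariates. Use GEE with robust standard errors, given the likely skew of the day counts.
3. Confirm that the ASI-Lite supplies the day count at intake and monthly, and state that the VAS is the instrument for the self-reported adherence outcome.
4. Reconcile *Assessments* with the randomization procedure so that the intake VAS and MOS-HIV are true pre-randomization values.
5. Align *Data Analysis to be reported in future publication* with the revised plan. If results are already known, label the adjusted models as added and report them beside the planned ones.

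The cost is one degree of freedom per model and a short edit to the text. No new data are needed.
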